1 INTRODUCTION

1.1 Ovarian Cancer background

Ovarian cancer (OC) has an annual incidence of 7500 women and causes 4100 deaths annually in the UK; the lifetime risk of developing OC is 1 in 56.¹ 70% of patients will present at advanced stage and all stage, 5 year survival rate is around 45%. OC is predominantly a disease of older, post-menopausal women, however 1000 women under 50 will be diagnosed with OC annually.^{1,17} An international cancer benchmarking project shows OC survival in the UK is significantly lower than other western countries; it is unclear as to whether this could be attributed to delay in diagnosis or differences in treatment received.^{1,2}

1.2 Current diagnosis of Ovarian Cancer

National Institute for Health and Care Excellence (NICE) guidelines in 2011 (last updated in 2023) recommended sequential testing using serum CA125 followed by pelvic ultrasound (USG) in women (particularly aged ≥ 50) presenting to primary care with symptoms on a persistent or frequent basis: persistent abdominal distension/'bloating', feeling full and/or loss of appetite, pelvic/abdominal pain, increased urinary urgency and/or frequency, unexplained weight loss, fatigue or changes in bowel habit²⁸. However these symptoms are very common^{3-6,11,16,20} with abdominal bloating alone being documented in 16-30% of women presenting to General Practitioners (GPs)⁷. Diagnostic challenges are considerable given (1) the low incidence of OC (a GP sees a woman with OC once in 3-5 years) (2) the low positive predictive value (PPV) of symptoms (only 1 in 400-600 symptomatic women have OC)^{8,9} and (3) the lack of clear diagnostic pathways. Furthermore, NICE guidelines do not detail what USG abnormalities should prompt referral²⁹.

Use of this NICE guidance is extremely variable. A survey of 258 GPs report that the majority would refer patients on the basis of raised CA125 even if the USG was normal¹⁰. Referrals were heterogeneous in symptoms and in what the GPs considered were abnormal levels of CA125 or abnormal USG. Two thirds of women referred were premenopausal. Women with complex masses considered benign can undergo laparoscopic or conservative management, whereas women with malignancy who undergo thorough surgery by gynaecological oncologist have the best outcomes^{12,13}. Therefore, there are compelling health needs to improve early detection^{19,20,25-27} and reduce cancer mortality whilst minimising unnecessary interventions in women.

1.3 The need for a new algorithm to test for OC

Earlier diagnosis of cancer has great potential to reduce mortality and morbidity. Recent technological advances allow tiny amounts of cancer signals including tumour-derived DNA and protein markers to be detected in blood samples. These methodologies have been utilised in recent years to develop cancer screening tests that are designed for the general population, driven by large commercial investments. There is a need to expand our understanding of the relationship between early cancer development and its representation in circulating tumour DNA (ctDNA) in blood plasma, to allow us to develop better analysis and detection tools for the future.

Routes to diagnosis data shows that currently OC diagnosis is made in women presenting through diverse routes – 2 week referrals, routine GP referrals, cross specialty referrals, with

a third of patients presenting as emergency presentations^{6,53}. Thus, risk prediction models must be assessed in a heterogeneous study population in all these settings.

1.4 The ROCKeTS GEN V2 project

ROCKeTS GEN validation study 2 evaluates ctDNA as a diagnostic test for ovarian cancer in women with non-specific abdominal symptoms. **This protocol refers to the ROCKeTS-GEN V2 study only.**

1.4.1 ROCKeTS GEN V2 prospective study

The ROCKeTS GEN V2 study: patients entering the study will donate a sample of blood – dried blood spot (~50-100ul), plasma (~9ml of blood) and serum samples. Patients who undergo surgery will have their histology details recorded for the study and representative tissue block will be collected for DNA isolation, for patients who do not undergo surgery wellbeing will be ascertained at 12 months follow-up after presentation by a clinic visit, a telephone call or by contacting GP. These data will be used at the end of the study.

FOR THE PURPOSE OF THIS PROTOCOL, THE TERM OVARIAN CANCER INCLUDES FALLOPIAN TUBE CANCER AND PRIMARY PERITONEAL CANCER.

1.5 Plasma circulating tumour DNA as a diagnostic biomarker for ovarian cancer

Using next generation sequencing (NGS) techniques it is now possible to amplify small amounts of free circulating DNA in the blood to identify molecular signals derived from the tumour. These tumour derived signals can include both genetic and epigenetic marks. Somatic mutations such as SNVs, SVs and copy number changes are highly specific biomarkers of cancer which can be used to detect circulating tumour DNA (ctDNA). The most commonly analysed epigenetic signal is DNA methylation which can be a reflection of tumour specific epigenetic events and will also reflect differences in representation of cell types in the blood which will change during disease processes such as carcinogenesis. Together these could provide a powerful non-invasive method for earlier cancer diagnosis^{24,30,31,32}. Other potential blood derived biomarkers would include the proteome.

The most common subtype of OC is high-grade serous ovarian cancer (HGSOC) which accounts for 70% of primary invasive epithelial ovarian cancers and the majority of mortality³³. To be useful as a diagnostic test a biomarker needs to be highly specific for the disease of interest and ubiquitous in the target population. The gene TP53 encodes the tumour suppressor protein p53, a transcription factor that regulates the expression of proteins involved in apoptosis and genomic integrity¹⁸. We have previously shown that mutations in TP53 occur in at least 99% of HGSOC cases^{34,35} making TP53 mutations ubiquitous in HGSOC. In HGSOC TP53 mutations are located throughout the gene in all 10 coding exons (exons 2 to 11) therefore a NGS method that is not limited to assaying hotspot mutations is required. To achieve a high level of sensitivity it is necessary to use as much blood as possible or to interrogate as many genomic positions as possible. TP53 mutation will only represent a single locus therefore limiting sensitivity, therefore we are making use of genome wide approaches these include the analysis of copy numbers HGSOC is also a tumour characterized by complex copy number changes³⁶ that can be detected by shallow whole genome sequencing (sWGS) which is a relatively inexpensive and easy to apply

methodology. sWGS data is also very appropriate data for the new and exciting field of fragmentomics. Fragmentomic analysis relies on the fundamental processes whereby cfDNA and ctDNA are generated by cleavage with specific enzymes and the accessibility of the DNA to these enzymes is dependent on the chromatin conformation. Therefore, there are valuable information contained within the cfDNA fragment ends, lengths and representation which can be used to enhance sensitivity of detection. Analysis of DNA methylation allows the interrogation of multiple loci genome wide or at higher depth restricted to a panel of selected loci these approaches have been demonstrated to enable the detection of cancer⁵¹ [for example *GRAIL studies*]⁵².

In preliminary analysis using samples from our previously conducted ROCKeTS-GEN study we have shown that a methylation based classifier developed by us can, even in women for whom there was no suspicion of ovarian cancer based on Risk of Malignancy Index (RMI, the standard of care test combining ultrasound and CA-125), with samples and data blindly analysed, 89% of women with stage III-IV ovarian cancer were correctly identified as cancer, while fewer than 20% of women without ovarian cancer were incorrectly identified as cancer, an error that could trigger further imaging by CT or MRI prior to surgery (unpublished data). This evaluation performance is based on blinded and statistically unbiased assessment of a subset of cases and controls from the ROCKeTS-GEN study. This includes approximately 30% of the cancers from the multi-centre study which recruited an unselected cohort of women immediately prior to surgery, where surgery was used to establish ovarian cancer status and disease staging. (Exact numbers and 95% confidence intervals are not reported here to protect the blinding of the main ROCKeTS-GEN trial analysis which is pending).

1.6. Other novel markers

Currently there is multiple promising biomarkers for early cancer detection including circulating tumor DNA (ctDNA)^{24,30,31}, microRNAs (miRNAs)³⁹, cancer glycomics^{48,49,50} and protein biomarkers^{40,41,44-46}, with emerging research exploring metabolites^{42,47} and epigenetic markers like DNA methylation⁴³. In ROCKeTS GEN V2, based on our developing understanding of technologies, we will analyse samples collected with some/all these technologies to try and identify the best biomarkers for OC.

1.6.1 ROCKeTS-GEN V2 Project

We propose to evaluate plasma ctDNA and collect additional samples suited for evaluation in the ROCKeTS-GEN V2 study by:

- 1) Collecting plasma samples and analysing ctDNA in a prospective cohort study (ROCKeTS-GEN V2) that will recruit **postmenopausal** participants
- 2) Collecting representative tissue blocks from resected tissue from patients undergoing surgery or biopsy so that the mutational profiles of plasma ctDNA can be verified against the mutational profile of tumours.
- 4) Collect additional samples of dried blood spot and serum which may be used in the future to improve diagnostic testing

1.7. Risks and Benefits

There are no vulnerable groups or risks associated with this project. There is no intervention, and all participants follow their normal care pathway.

2 ROCKETS GEN V2 STUDY DESIGN

2.1 Aim of the study

- To evaluate plasma ctDNA as a diagnostic test with increased sensitivity and specificity compared to serum CA125 for earlier diagnosis of ovarian cancer in postmenopausal women.
- To collect representative blocks from resected tumour tissue to establish a translational resource for future early detection research.
- To collect dried blood spots and serum for analysis of circulating biomarkers and blood ctDNA in cohorts of women at high risk of ovarian cancer, to establish improved diagnostic test for postmenopausal women.

2.2 Design

ROCKETS GEN V2 study is a prospective single arm cohort diagnostic accuracy study where all patients receive all tests and accuracy of tests is evaluated against a gold standard of histology or 12-month outcome.

A test accuracy study compares measurements obtained by index tests with those obtained by a reference standard. In this way the accuracy of index tests can be estimated. A reference standard is a test (or combination of tests) that confirms or refutes the presence or absence of disease beyond reasonable doubt.

Here, the reference standard will be histology or cytology of tissues taken from patients who proceed to surgery or biopsy, or in patients who do not undergo surgery or biopsy assessment of cancer/non cancer outcomes determined from hospital records at 12 months. The diagnostic performance of the index test will be compared against that of the comparator test – the existing standard risk prediction score RMI 1. RMI combines CA125 and limited ultrasound features to provide a score that is used to determine patient management.^{3,37}

ROCKETS GEN V2 will recruit postmenopausal women at 'low' or unknown genetic risk of ovarian cancer i.e. not women known to have a BRCA1/2 or other germline mutation predisposing to ovarian cancer.

Recruited women will have the following tests and follow up recorded:

- CA125 (if not performed already as part of standard care).
- IOTA transvaginal ultrasound and additional abdominal scan if performed as part of standard care
- Histology result where biopsy or surgery is clinically indicated
- 12 month follow up status ascertained by research team using hospital records, a telephone call or by contacting GP.
- Women entering ROCKETS-GEN V2 will donate dried blood spots, blood samples for plasma and serum analysis at recruitment. Women undergoing surgery for ovarian pathology will also be consented to donate tissue block/s of representative tissue for research.

Representative tissue block/s and slide will be retrieved from pathology labs and proceeding to undergo surgery as part of standard care. These blocks will first undergo specialist pathology review by an expert gynaecological pathologist. DNA will then be extracted from cancer tissues for additional analyses including shallow whole genome sequencing.

In ROCKeTS GEN V2, the index tests (ctDNA analysis) will be externally validated at the end of the study. Therefore, we will collect dried blood spots, serum and plasma in the study to be analysed and validated at the end of the study.

2.3 Setting

Recruiting from NHS sites within the UK. Secondary care outpatients: 2 week referrals, USG clinics, routine GP referrals, cross specialty referrals, preadmission clinics. Inpatients: emergency presentations to secondary care.

2.4 Target Population

Postmenopausal women who have been referred to secondary care with symptoms of suspected OC.

Symptoms are as defined by NICE which include but are not restricted to persistent or frequent abdominal distension, feeling full (early satiety) and/or loss of appetite, pelvic or abdominal pain, increased urinary urgency and/or frequency. Symptoms listed here are not an exhaustive list.

2.5 Comparator for ROCKeTS GEN V2

RMI at cut off 200³⁷.

2.6 Analysis

Plasma ctDNA analysis at Cancer Molecular Diagnostic Laboratory (CMDL) will be performed blind from tissue DNA analysis. Sensitivity and specificity of plasma ctDNA will be established by statistical analysis. Blood and dried blood spot samples will be stored and analysed for multiple analytes such as proteins, by CMDL and QMUL. The genomic methodology will be used, including whole genome sequencing. ROCKeTS-GEN v2 uses a rapidly changing technology for analysis and therefore exact detail on how the analysis will be performed will not be detailed in the protocol but will be detailed in full in the final report and any publications.

2.7 Reference standard

Reference standard for the study will be histology of tissue taken at surgery or biopsy or cytology in postmenopausal women who are managed surgically following study enrolment or assessment of wellbeing at 12 months after presentation for patients who do not undergo surgery.

Study data collection will be undertaken prospectively for all participants in order to inform the costs for each pathway. Following giving consent at baseline, the participants and the local study team will complete a series of CRFs (see table 1) including:

- 1) Participant Baseline CRF

2) Registration form

3) A surgery CRF will be completed where histology is attempted from tissue taken at surgery or biopsy or cytology. Should histology from one of these procedures come back as unknown but is identified at a later date from a subsequent surgery/histology, the surgery CRF should be updated. The surgery CRF will be completed by the research team.

If no surgery CRF has been completed by 12 months post study entry, a 12 month Clinical CRF will be completed by the research team after either a clinic visit or a telephone call to the participant or from medical records.

If insufficient information is available through the medical records, the GP will be contacted to ensure that all available data are collected.

Participation in the ROCKETS GEN V2 study is completed on receipt of a completed surgery CRF. If the participant does not have surgery, then completed 12 month Clinical CRFs will indicate completion.

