2.10 Schedule of Events & CRF completion for ROCKETS-GEN V2

Table 1: Schedule of events and CRF completion

	Screening	Baseline	≤ 12 months
Eligibility Check	x ¹		
Valid Informed Consent	x ¹		
Registration Form CRF		x	
Online registration		x ²	
GP Letter		x	

Blood sample		x ⁴	
IOTA USG		Optional	
Ultrasound CRF		Optional	
Participant Baseline CRF		x ³	
Surgery CRF			Post-surgery/biopsy
Representative tissue block/s			x ⁵
Outcome CRF			12 months – only required if histology/cytology not obtained

¹ See section 'Approaching Potential Participants to Consent'.

² It is acceptable to delay registration until blood sample, IOTA USG & Participant Baseline CRF are complete.

³ Blood sample, IOTA USG and Participant Baseline CRF should all be captured within 3 months of whichever of the following occurred first: presentation, IOTA USG (see section 5.1).

⁴ Blood samples including dried blood spots, serum and plasma, send immediately to CMDL

⁵ Tissue sample (if participant proceeds to surgery) or biopsy send to Central study lab (CMDL or QMUL).

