5.2 Reference standard/Follow-up schedule

Reference standard for the study will be histology of tissue taken at surgery or biopsy or cytology in women who are managed surgically following study enrolment. Outcome of participants referred for suspected OC that do not undergo surgery will be assessed by a follow-up visit at 12 months or by a telephone call from the research team at 12 months, as per the local investigators' discretion and clinical assessment. Wellbeing will be ascertained at this follow-up.

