5.3 Study duration

For **ROCKeTS GEN V2 participants** we anticipate recruitment of 500 participants. The current recruitment end date for ROCKeTS is 3 years from when the study is open at sites. It is anticipated that the recruitment will take 2 years. The follow-up will be 12 months from recruitment of last patient.

As per protocol, where histology is unavailable, participants should be followed up for the full 12 months, however the study recognises that for participants recruited within the last 12 months of the recruitment period the full 12 month follow-up will not be possible; instead, these participants should only be followed up until the end of study period.

The end of the ROCKeTS GEN V2 study, will be the date of the last data capture including sample analysis and resolution of all data clarification forms. This will allow sufficient time for the completion of protocol procedures, data collection and data input. The Trial Office will notify the REC and the Sponsor within 90 days of the end of trial. Where the trial has terminated early, the Trial Office will notify the REC within 15 days of the end of trial. The Trial Office will provide the REC and the Sponsor with a summary of the clinical trial report within 12 months of the end of trial.

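### Conflicting triggers for the 12-month form leave women with only a benign or non-diagnostic biopsy or cytology without a settled cancer check, and the fallback outcome is worded in two ways

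*Protocol*

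**What the plan says.** Protocol section 2.7 contains three linked rules.

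- What creates the form: "A surgery CRF will be completed where histology is attempted from tissue taken at surgery or biopsy or cytology".
- What ends participation: "Participation in the ROCKETS GEN V2 study is completed on receipt of a completed surgery CRF". No condition is placed on the result.
- What triggers the later form: "If no surgery CRF has been completed by 12 months post study entry, a 12 month Clinical CRF will be completed".

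Section 2.7 also has an update rule. "Should histology from one of these procedures come back as unknown but is identified at a later date from a subsequent surgery/histology, the surgery CRF" is to be updated. The sentence directly after the completion rule says that for a participant without surgery, the 12-month form marks completion. Sections 1.4.1 and 5.2 likewise assess women at 12 months when they have had no surgery.

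Elsewhere the trigger differs. In Table 1 (section 2.10) the Outcome CRF at 12 months is "only required if histology/cytology not obtained". Section 5.3 says "where histology is unavailable, participants should be followed up for the full 12 months".

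On the content of the fallback, section 5.2 says "Wellbeing will be ascertained at this follow-up". Sections 1.4.1, 2.7 and 5.5 use the same term, and 5.5 adds that the template for it is still to be developed. Section 2.2 instead defines the fallback as a cancer or non-cancer outcome taken from hospital records at 12 months.

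**The concern.** In a diagnostic accuracy study the reference standard decides which women count as diseased. A biopsy or cytology sample can miss a lesion, and a non-diagnostic sample gives no answer. If such a sample ends data collection, nobody looks for a later diagnosis.

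A cancer labelled negative in this way distorts the results in one of two directions. If ctDNA was positive, she is scored as a false positive and specificity is understated. If ctDNA was negative, she is scored as a true negative and sensitivity is overstated. The same applies to the comparator, RMI 1.

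The fallback wording raises a related problem. Wellbeing is not a disease status, and no rule in the protocol turns it into cancer or no cancer.

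**Working it through.** **The triggers side by side.** I take the 12-month Clinical CRF of 2.7 and the Outcome CRF of Table 1 to be the same form. Is a 12-month assessment due?

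| Woman's situation | 2.7, no surgery CRF | 2.7 next sentence, 1.4.1, 5.2 (no surgery) | Table 1 | 5.3 |
|---|---|---|---|---|
| Benign biopsy only | No | Yes | No | No |
| Benign cytology only | No | Yes | No | Yes, read literally (no histology) |
| Non-diagnostic biopsy or cytology, no later procedure | No | Yes | Yes, if 'obtained' means a result | Yes |
| No sample at all | Yes | Yes | Yes | Yes |

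Only the last row is consistent. In the first row, Table 1 does not supply the missing form, because histology was obtained. In the third, the update rule helps only if a later procedure happens and its result reaches the study. No active check is planned to find it.

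**The protocol's own counts** (sections 2.8 and 5.7.2: 500 women, 5% lost, 10–15% without surgery or biopsy, about 406 analysed, 27% prevalence, 110 cancers).

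1. After losses: 500 × 0.95 = 475.
2. Analysed: 475 × 0.90 = 427.5 at the 10% end and 475 × 0.85 = 403.75 at the 15% end. The stated 406 corresponds to 14.5%: 475 × 0.855 = 406.1. The figure is reproduced near the top of the range.
3. Cancers: 406 × 0.27 = 109.6, or 110.
4. Sampled women not expected to have ovarian cancer: 406 − 110 = 296. Women with only a benign or non-diagnostic biopsy or cytology fall within this group, as do all those whose lesion was surgically removed. So 296 is a ceiling on the women exposed to the gap, not an estimate.
5. Women with neither surgery nor biopsy: 475 × 0.10 = 47.5 to 475 × 0.15 = 71.25, or about 48 to 71. They are the main users of the fallback outcome, and they are already outside the 406.
6. Primary target, early-stage HGSOC: 110 × 0.70 × 0.25 = 19.25, or about 19.

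The next step would be the share of the 296 with only biopsy or cytology, multiplied by the rate at which such results prove wrong. The protocol gives neither figure.

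**The case against.** The strongest reply is that the protocol as a whole follows these women.

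- **Non-diagnostic samples.** The update rule, Table 1 and 5.3 all point towards continued follow-up. This stands: a reader might infer from 2.7 that any failed sample simply closes the case, and the document does not say that. What remains is a conflict with the 2.7 trigger, and no active check.
- **Benign biopsy or cytology.** Such a woman has had no surgery, so the next sentence of 2.7, with 1.4.1 and 5.2, can be read as requiring the 12-month form. This also stands. Closure is one reading among several, not a settled rule. But 2.7's trigger and Table 1 both point the other way for her.
- **Wellbeing.** Section 2.2 states the right outcome, Table 1 calls the form an Outcome CRF, and its content is still open. It would therefore be wrong to say that the study measures wellbeing instead of cancer status. The defect is that the sections describing follow-up and form content disagree with the design section.
- **Imputation.** Section 5.7.1 plans it for missing and imperfect reference data, and the method may be set out in a SAP that is not shown. It is unlikely to close this gap. A woman recorded as benign is not flagged as missing, and no later outcome would have been collected to inform the imputation.

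**Conclusion.** The concern holds as an internal contradiction with a verification gap. The conflicting passages are 1.4.1, 2.2, 2.7, 5.2, 5.3, 5.5 and Table 1. The gap affects women whose only sample is a benign, unknown or non-diagnostic biopsy or cytology. It bears on the planned 406, because these women are counted there. The wellbeing wording has little effect on that number, because 5.7.2 already leaves out the 10–15% who mainly rely on it. It still matters for the study's stated design, which includes the 12-month outcome in the reference standard.

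Three stronger readings are tempting but unsupported.

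- That the reference standard does miss cancers, in some stated number. Without a split of sample types and an error rate, this is a risk of unknown size.
- That each missed early HGSOC costs one nineteenth of sensitivity (1/19 = 5.3 points). A recovered case also enlarges the denominator. If 15 of 19 were detected (78.9%, an illustration only), one more case gives 16/20 = 80.0% or 15/20 = 75.0%. Nor would every missed cancer be early HGSOC: on the protocol's shares that is 0.70 × 0.25 = 17.5% of ovarian cancers.
- That the misses fall mainly on small early lesions. No section supports this.

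The point still deserves correction before data collection, because a check that was not made cannot be recovered at analysis.

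**What to change.** Reconcile sections 2.2, 2.7, 5.2, 5.3 and Table 1 into one data-collection trigger for the 12-month Outcome CRF, and bring 1.4.1 and 5.5 into line. The trigger should cover women with no sample and also those whose only sample is a benign, unknown or non-diagnostic biopsy or cytology. The form should be completed from records where possible, and the completion rule in 2.7 should say that a surgery CRF alone does not end data collection for these women.

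Replace wellbeing as the reference outcome with the one in 2.2, recorded as ovarian cancer yes, no or unknown. Write this into the template that 5.5 leaves to be developed.

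The cost is one records check at 12 months for a subset of women, on a form that already exists and that 2.7 already allows to be completed from medical records. It adds no visit or procedure and does not change clinical care.
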